133 consideration as well. In addition to the definition provided above, participants were
134 considered to have received additional treatment if there was an increase in the prism
135 prescription after enrollment. Participants were considered to have received additional
136 treatment at 10 weeks if the treatment history form at 10 weeks indicated that the
137 magnitude of the prism prescription had increased since enrollment. Participants were
138 considered to have received additional treatment at 12 months if the treatment prescribed
139 form at 10 weeks or the treatment history form at 12 months indicated that the magnitude
140 of prism prescribed had increased since enrollment.

141 Surgery group

142 Participants who were prescribed surgery at enrollment were considered to have received
143 additional treatment if the treatment history form at 10 weeks indicated that Botox or
144 surgery was received prior to the office visit. Participants were considered to have
145 received additional treatment at 12 months if the treatment prescribed form at 10 weeks
146 or the treatment history form at 12 weeks indicated that Botox, orthoptic exercises, prism,
147 or surgery was prescribed or received.

148 **5.0 Primary Analysis**

149 The following were tabulated by treatment prescribed at enrollment:

- 150 • The number and proportion of participants who met success criteria at distance
151 (see Section 1.3) at 10 weeks
- 152 • The number and proportion of participants who met success criteria at distance
153 (see Section 1.3) at 12 months

154 A 95% Clopper-Pearson confidence interval was calculated for each proportion.

159 Participants were included in analysis only if the DQ was completed at the visit. There
160 was one exception to this rule, participants were considered a failure if additional
161 treatment was received prior to the visit. If the 10-week treatment history form indicated
162 that additional treatment was received prior to the 10-week visit, the participants was
163 considered a failure both at 10 weeks and at 12 months. If the 12-month treatment history
164 form or the 10-week treatment prescribed form indicated that additional treatment was
165 received prior to the 12-month visit, then the participant was considered a failure at 12
166 months. When additional treatment was received prior to the visit, the participant was
167 counted in the denominator but not the numerator when calculating the success

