168 proportion. It is acknowledged that this procedure is biased unless the 10-week and 12-
169 month DQ data are not missing at random (NMAR), with those who missed that visit
170 being in truth more likely to be failures than those who completed the visit. In that case,
171 this procedure may be less biased. If the data are missing completely at random (MCAR),
172 the resulting estimate of success is an underestimate.

173

174 **6.0 Secondary Analyses**

175 Data collected after additional treatment was received was no longer representative of the
176 treatment initiated at enrollment. Consequently, data were excluded from analyses and
177 tabulations if additional treatment was prescribed or received prior to the visit, unless
178 otherwise specified.

179

180 **6.1 Number and Proportion of Participants that Received Each Treatment**

181 The number and proportion of participants that were prescribed each treatment at
182 enrollment was tabulated. Participants who were re-enrolled will be counted twice: once
183 for the initial treatment (orthoptic exercises or prism) prescribed at enrollment and again
184 for the second treatment (Botox or surgery), prescribed at re-enrollment.

185

186 **6.2 Participant characteristics at Enrollment and Medical History**

187 The following characteristics reported at enrollment were tabulated according to the
188 treatment initiated at enrollment:

189

- 190 • Sex
- 191 • Race/Ethnicity (White versus non-White)
- 192 • Age (18-24, 25-34, 35-44, ..., 75-84, 85-91)
- 193 • Whether or not refractive correction (spectacles or contact lenses) was
194 worn at the office visit
- 195 • Prior treatment for strabismus (orthoptic exercises, prism, none)
- 196 • Coexisting neurological conditions (Parkinson's, progressive supranuclear
197 palsy, basal ganglia disease, stroke, intracranial tumor)
- 198 • Other conditions (epiretinal membrane; age-related macular degeneration;
199 macular pathology; heart disease; diabetes; autoimmune disease;
200 significant head trauma; hypertension; cancer of bladder, breast, or
201 prostate)

201

202 The mean, standard deviation, median, and interquartile range (IQR) will be calculated
203 for age at enrollment.

204

205 **6.3 Clinical Characteristics at Enrollment**

206 The following clinical characteristics measured at enrollment were tabulated according to
207 the treatment initiated at enrollment:

- 208 • Frequency of diplopia at distance during the last week

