- 209 • Frequency of diplopia in reading position during the last week
- 210 • Horizontal deviation at distance (measured using PACT)
- 211 • Horizontal deviation at near (measured using PACT)
- 212 • Whether or not prism was needed to fuse in free space at distance

213

214 The mean, standard deviation, median, and IQR were tabulated for the following:

- 215 • Horizontal deviation at distance (measured using PACT)
- 216 • Horizontal deviation at near (measured using PACT)
- 217 • DQ score
- 218 • Adult-Strabismus (AS-20) general function score
- 219 • AS-20 reading function score
- 220 • AS-20 self-perception score
- 221 • AS-20 interaction score

222

223 **6.4 Secondary Definition of Success: Successful Treatment at Both Distance and**
224 **Near**

225 Successful treatment at both distance and near is defined as diplopia reported “rarely” or
226 “never” both in the reading position and in the distance, and no additional treatment
227 prescribed.

228

229 The following were tabulated by treatment prescribed at enrollment:

- 230 • The number and proportion of participants who met success criteria at both
231 distance and near at 10 weeks
- 232 • The number and proportion of participants who met success criteria at both
233 distance and near at 12 months

234

235 A 95% Clopper-Pearson confidence interval was calculated for each proportion.

236

237 Participants were included in analysis only if the DQ was completed at the visit. There
238 was one exception to this rule. If the treatment history form or the treatment prescribed
239 form at the 10-week visit indicated that additional treatment was received, then the
240 participant will be considered a failure at 12 months. It is acknowledged this procedure
241 may be biased (see Section 4.0).

242

243 **6.5 Successful Treatment within Prism and Surgery Subgroups**

244 The following were tabulated within prism and surgery treatment subgroups:

- 245 • The number and proportion of participants that met success criteria at distance at
246 10 weeks
- 247 • The number and proportion of participants that met success criteria at both
248 distance and near at 10 weeks

- 249 • The number and proportion of participants that met success criteria at distance at
250 12 months
251 • The number and proportion of participants that met success criteria at both
252 distance and near at 12 months
253

254 A 95% Clopper-Pearson confidence interval was calculated for each proportion.
255

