256 Participants were included in analysis only if the DQ was completed at the visit. There
257 was one exception to this rule: participants were considered a failure if additional
258 treatment was received prior to the visit. It is acknowledged this procedure may be biased
259 (see Section 5.0).
260

261 **6.6 Secondary Clinical Outcomes**

262 The following statistics will be calculated to describe the DQ score and each AS-20
263 subscale score at each visit, according to the treatment initiated at enrollment:

- 264 • Mean score at visit and standard deviation
265 • Mean change in score from enrollment and the corresponding 95% confidence
266 interval
267

268 These statistics were also calculated according to treatment subgroups.
269

270 **6.7 Treatment Success for Participants Enrolled into the Surgery Group by 271 Whether Prism was Prescribed Prior to Enrollment or No Prior Treatment was 272 Reported**

273 The following were tabulated for participants who were prescribed surgery at enrollment
274 according to whether prism was prescribed prior to enrollment or no treatment was
275 prescribed prior to enrollment:

- 276 • The number and proportion of participants that met success criteria at distance at
277 10 weeks
278 • The number and proportion of participants that met success criteria at both
279 distance and near at 10 weeks
280 • The number and proportion of participants that met success criteria at distance at
281 12 months
282 • The number and proportion of participants that met success criteria at both
283 distance and near at 12 months
284

285 A 95% Clopper-Pearson confidence interval was calculated for each proportion.
286

287 Participants were included in analysis only if the DQ was completed at the visit. There
288 was one exception to this rule: participants were considered a failure if additional
289 treatment was received prior to the visit. It is acknowledged this procedure may be biased
290 (see Section 5.0).

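### SAP 6.4 gives a narrower failure rule for treatment changers than 5.0, 6.5 and 6.7, so the stricter distance-and-near success rate can rest on a smaller denominator than the primary rate

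*SAP*

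**What the plan says.** Here a changer is a participant with additional treatment after enrolment, and DQ is the diplopia questionnaire.

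- **SAP 1.3 and 5.0 (primary, distance).** Success requires diplopia no more than rarely at distance and no additional treatment received before the visit. Only participants with a DQ at the visit are analysed, except that changers fail. A change on the 10-week history form means failure at both visits. A change on the 12-month history form or the 10-week prescribed form means failure at 12 months. Changers are "counted in the denominator but not the numerator when calculating the success" proportion.
- **SAP 6.0 (default for secondary analyses).** Data are left out of analyses and "tabulations if additional treatment was prescribed or received prior to the visit, unless" a section provides otherwise.
- **SAP 6.4 (distance and near, overall).** Success requires diplopia no more than rarely "both in the reading position and in the distance, and no additional treatment" prescribed. DQ completers only, with one exception: if the history form or the prescribed "form at the 10-week visit indicated that additional treatment was received, then the" participant fails at 12 months. Nothing is said about the 10-week rate or the 12-month history form.
- **SAP 6.5 and 6.7 (distance, and distance and near, in subgroups).** The general rule returns: there "was one exception to this rule: participants were considered a failure if additional" treatment came before the visit.

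**The concern.** Success at both distance and near is meant to be a subset of success at distance. On a common set of participants its rate cannot be the higher of the two. SAP 6.4 breaks the common set in two places: changers flagged on the 10-week history form, for the 10-week rate, and changers flagged only on the 12-month history form, for the 12-month rate. Under 5.0 both groups are failures. Under 6.0 read with 6.4 they disappear.

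The same outcome then has one denominator rule in its overall table (6.4) and another in its subgroup tables (6.5, 6.7). A reader comparing the primary rate with the 6.4 rate could conclude that adding near diplopia to the criterion costs little or nothing, when the difference comes from who was counted.

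**Working it through.** **The plan's own figure.** Neither SAP section states a denominator or a rate. The nearest planning figure is in Protocol 5.2: 50 per group with up to 5% loss gives 50 × 0.95 = 47.5, stated as about 47, and a maximum 95% half-width of 1.96 × √(0.25/47) = 14.3 points, stated as 14%. Both reproduce. I use N = 47 only as an illustrative primary denominator; the SAP tabulates by treatment modality, so actual group sizes may differ.

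**Who is counted**

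| Changer flagged on | Visit | 5.0, 6.5, 6.7 | 6.4 read with 6.0 | 6.4 if its definition overrides 6.0 |
|---|---|---|---|---|
| 10-week history form | 10 weeks | failure | dropped | failure if DQ done, otherwise dropped |
| 10-week history or prescribed form | 12 months | failure | failure | failure |
| 12-month history form only | 12 months | failure | dropped | failure if DQ done, otherwise dropped |

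**Algebra.** Let S1 be distance successes, S2 both-successes (S2 ≤ S1), and k the changers that 5.0 fails but 6.4 drops. Dropped changers are in neither numerator.

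- Primary rate: S1/N.
- Stricter rate under the 5.0 rule: S2/N, which can never exceed S1/N.
- Stricter rate under 6.4: S2/(N-k), larger than S2/N by the factor N/(N-k).
- Reversal: S2/(N-k) > S1/N, which rearranges to S1 - S2 < S1 × k/N.

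**Illustration (counts assumed): N = 47, S1 = 30, S2 = 29.** Primary: 30/47 = 63.8%. Stricter rate under the 5.0 rule: 29/47 = 61.7%. Reversal needs 1 < 30k/47, so k of at least 2.

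| k | 6.4 rate | Excess over 61.7% | Above primary 63.8%? |
|---|---|---|---|
| 1 | 29/46 = 63.0% | 1.3 points | no |
| 2 | 29/45 = 64.4% | 2.7 points | yes |
| 3 | 29/44 = 65.9% | 4.2 points | yes |

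**Other assumed success levels**, with k = 3 and one distance success lost at near:

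- S1 = 33: 32/44 = 72.7% against 33/47 = 70.2%, reversal.
- S1 = 24: 23/44 = 52.3% against 24/47 = 51.1%, reversal.
- S1 = 15: 14/44 = 31.8% against 15/47 = 31.9%, no reversal.

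Reversal is therefore easier when success is common and near diplopia rarely removes a success. With k = 1 it occurs only if S2 = S1.

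**Subgroups.** If one rule applied throughout, the overall surgery rate would be a weighted average of the rates by surgery type and could not exceed all of them; under 6.4 it can. The prism group does not allow this check. SAP 4.0 counts an increase in prism as additional treatment within prism subgroups only, so the overall prism rate can exceed every prism subgroup rate by design.

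**The case against.** The strongest reply is that 6.4 does have a failure rule at both visits, inside its definition of success. Someone prescribed additional treatment cannot be a success, the outcome is tabulated at 10 weeks and 12 months, and a definition that scores additional treatment is arguably the kind of specification to which 6.0 yields. If 6.0 had already removed changers, that clause would be largely redundant. The exception sentence would then deal only with people who have no DQ. This reading is reasonable, and the text does not settle between it and exclusion.

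On that reading k shrinks to changers outside the exception who have no DQ at the visit. They may be few. Under Protocol 3.3 treatment data and the DQ are collected at the same visit, with questionnaires first, and the early outcome exam in Protocol 3.5 follows 3.3 and so includes the DQ. Protocol 3.5 does end participation after some changes, but the documents do not say how an exam between scheduled visits maps to the visit forms, so it cannot be used to claim that such cases are common.

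The direction is not one-sided either. The definition in 6.4 says prescribed where 1.3 and 5.0 say received before the visit. It may therefore fail someone whom 5.0 counts as a success, which lowers the 6.4 rate.

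What the reply does not remove: 5.0, 6.5 and 6.7 keep changers without a DQ in the denominator in general, and 6.4 keeps only some of them. Under the exclusion reading the affected group is wider. For example, a surgery participant who adds prism after the 10-week visit is followed to 12 months under Protocol 3.5, is a failure in 5.0, and is dropped by 6.0 with 6.4.

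**Conclusion.** The inconsistency is in the text and worth correcting. SAP 6.4 as written can place a nested outcome on a smaller denominator than its parent in 5.0, and under a different rule from its own subgroup tables in 6.5 and 6.7.

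The size is unknown, because the documents give neither k nor the success counts. In the illustration the inflation is 1.3 to 4.2 points for k = 1 to 3, well inside the 14-point half-width for a group of 47. The harm is to the coherence of the two tables rather than to precision.

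Three stronger readings are not supported:

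- A reader might infer that the 6.4 rate does exceed the primary rate. It can, but only if at least one changer falls outside the exception and S1 - S2 < S1 × k/N. If no changer does, nothing changes.
- A reader might infer that all changers in these two groups are certainly dropped. That holds only if 6.0 prevails over the definition in 6.4.
- A reader might extend the subgroup comparison to prism. SAP 4.0 rules that out; it applies to surgery.

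**What to change.** 1. In SAP 6.4, replace the exception with the 5.0 rule: additional treatment received before a visit means failure at that visit and later, kept in the denominator at 10 weeks and 12 months, with the 12-month history form named.
2. In the 6.4 definition, use the wording of 1.3 and 5.0 (received before the visit) in place of prescribed. Without this the two outcomes still differ after step 1.
3. State in 6.0 that its exclusion does not apply to the success proportions in 6.4, 6.5 and 6.7.
4. Report both outcomes with their denominators, on the same set apart from participants missing the reading item.
5. Correct the cross-reference on bias in 6.4: it points to Section 4.0, but the discussion is in 5.0, as 6.5 and 6.7 say.

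The cost is SAP wording and one rerun table, with no new data. The 6.4 percentages may become slightly less favourable. If the program already applies the 5.0 rule, the correction is to the text only. The SAP's version history says it was completed after a first manuscript draft, so the denominators used can be checked directly.
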